8.3.4 Menstrual Bleeding

Menstrual bleeding is only to be reported as an adverse event in case it is excessive, painful, delayed or in any other way deviating from the subject's normal menstruation. Menstrual bleeding associated with lack of pregnancy will be reported as part of the efficacy evaluation.

8.3.5 Ovarian Torsion

Any case of ovarian torsion will be reported as an adverse event and it will be specified whether it is associated with any signs or symptoms of OHSS.

8.4 Serious Adverse Events

8.4.1 Serious Adverse Event Definition

Serious Adverse Events during the Trial

An event is defined as a serious adverse event if it:	Guidance
results in death	-
is life-threatening	The subject was at immediate risk of death at the time of the event. The criterion does not refer to an event which might hypothetically have caused death if it were more severe.
requires hospitalisation	Hospitalisation is defined as requiring in-patient admission to hospital or as prolongation of existing hospitalisation as a result of an event.
results in persistent or significant disability/incapacity	Disability / incapacity means a substantial disruption of a person's ability to conduct normal life functions. In doubt, the decision should be left to medical judgement by the investigator.
is a congenital anomaly/birth defect	Observed in any offspring of the subject conceived during treatment with the IMP.
is an important medical event	Medical and scientific judgment should be exercised in deciding whether other situations should be considered serious such as important medical events that might not be immediately life-threatening or result in death or hospitalisation but might jeopardise the patient or might require intervention to prevent one of the other outcomes listed in the definition above. Examples of such events are intensive treatment in an emergency room or at home for allergic bronchospasm, blood dyscrasias or convulsions that do not result in hospitalisation, or development of drug dependency or drug abuse.

Serious Adverse Events during Pregnancy Follow-up

Pregnancy outcome will be collected for all subjects with an ongoing pregnancy, as a follow-up to the current trial. Furthermore, neonatal health data will be collected at birth (i.e. data reported on the day of birth [day 0] or the day after [day 1]) and at 4 weeks after birth (reported between day 2 and day 28 [both inclusive]).

The following untoward medical occurrences reported as part of the pregnancy follow-up will be recorded as SAEs:

- Death of mother in connection with pregnancy or labor
- Death of neonate
- Stillbirth^e
- Neonate admitted to the neonatal intensive care unit (NICU) regardless of duration, or neonate admitted to the neonatal care unit (NCU) for more than 2 hours^f

^e Stillbirth: gestational age \geq 24 weeks + 0 days, calculated from the day of day 3 embryo transfer + 17 days.

^f Only classifies as SAE if NICU / NCU admission is due to medical reasons, i.e. NICU / NCU admission due to hospital protocol only does not classify as SAE.

- Congenital anomaly / birth defect
- Important medical event in the neonate

In case of admission to NICU or NCU, the reason for admission must be reported as an SAE, rather than just the act of hospitalisation.

Congenital anomalies are defined as abnormalities of body structure or function that are present at birth and are of prenatal origin. For some congenital anomalies (e.g. patent ductus arteriosus or undescended testes), the case definition may vary depending on gestational age at delivery, i.e. they may be considered physiological among preterm neonates. Nevertheless, all abnormalities of body structure or function – both minor and major, detected in fetuses/neonates, and all events in doubt, regardless of other confounding factors like preterm birth – are to be reported as SAEs with the seriousness criterion ‘congenital anomaly’ for the purpose of safety surveillance. Congenital anomalies will be coded by Ferring using both MedDRA and International Classification of Diseases (ICD) and classified as minor or major [Note: congenital post-mortem findings following a pregnancy loss should not be reported as SAEs].

8.4.2 Collection, Recording and Reporting of Serious Adverse Events

SAE Reporting by the Investigator

All SAEs must be communicated **immediately** to Ferring Pharmacovigilance as soon as it becomes known to the investigator and not later than within 24 hours of their knowledge of the occurrence of an SAE.

The investigator is responsible for providing the completed and signed SAE Report Form with the fullest possible details **within 5 calendar days** of his/her knowledge of the SAE. In case collected follow-up information leads to changes in the investigator causality assessment, the investigator must re-sign the SAE form.

The same timelines apply for both the SAE Report Form and any follow-up with additional information regarding the SAE, i.e. 24 hours within obtaining knowledge of the follow-up information and 5 calendar days for providing the fullest possible details.

Serious Adverse Event Report Form

The SAE Report Form is included in the EDC system and must be completed and submitted according to the instructions provided on the form. In case the EDC system cannot be accessed and hence the SAE Report Form cannot be filled in within the EDC system, a paper SAE Report Form should be used and sent to Ferring Pharmacovigilance using the contact details below.

Global Pharmacovigilance, Ferring Pharmaceuticals A/S
E-mail: [contact]
Fax: ([contact]

Completion of the Demographics, Adverse Event Log, Medical History Log and Concomitant Medication Log are mandatory for initial reports and for follow-up reports if any relevant changes have been made since the initial report. Data entries must have been made in the EDC system for Ferring Pharmacovigilance to access the information.

Additional information relevant to the SAE such as hospital records, results from investigations, e.g. laboratory parameters (that are not already uploaded in the EDC system), invasive procedures, scans and x-rays, and autopsy results can be faxed or scanned and e-mailed to Ferring Pharmacovigilance using the contact details in the section above. In any case this information must be supplied by the investigator upon request from Ferring. On any copies provided, personal details such as subject's name, address, and hospital name should be concealed and instead subject number should be provided.

The investigator will supply Ferring and the ethics committees with any additional requested information.

Overdose and medication errors of IMP with and without clinical consequences will be tracked in the EDC and reviewed by Ferring Pharmacovigilance on an ongoing basis.

Expedited Reporting by Ferring

Ferring will report all adverse events according to local regulations.

8.5 Follow-up of Adverse Events and Serious Adverse Events

8.5.1 Follow-up of Adverse Events with Onset during the Trial

During the trial, the investigator must follow-up on each adverse event until the subject's last visit. After the subject's last visit, the investigator must follow-up on any adverse event classified as serious or considered to have a reasonable possible causality to the IMP until it is resolved or until the medical condition of the subject is stable. All such relevant follow-up information must be reported to Ferring. Follow-up should continue until the outcome of recovered, recovered with sequelae, or fatal, has been reached. If the event is considered stable or a chronic condition, the investigator and Ferring may agree that further follow-up is not required.

8.5.2 Collection of Serious Adverse Events with Onset after Last Visit in the Trial

If an investigator becomes aware of an SAE after the subject's last visit, diagnosed either to the subject herself or to the fetus / neonate, and investigator assesses the SAE to have a reasonable possible causality to IMP (FE 999049 or GONAL-F) or NIMP where Ferring is Marketing Authorisation Holder (DECAPEPTYL), the case will have to be reported to Ferring (see

Section 8.4.2), regardless how long after the end of the trial this takes place.

8.5.3 Follow-up of Serious Adverse Events in Neonates

During the follow-up of neonatal health, any serious adverse event reported as not recovered at the 4-weeks follow-up assessment must be followed by the investigator until the SAE has resolved. If the SAE is a chronic condition or the medical condition of the neonate is stable, the investigator and Ferring may agree that further follow-up is not required.

8.6 Technical Complaints

A technical complaint can include but is not limited to problems with dose delivery, the packaging material (e.g. label text is not legible) or the physical appearance of a trial product (e.g. particles or discoloration).

If a technical complaint is identified, the investigator must assess whether it may be associated with an adverse event and/or a medication error. Technical complaints are reported in accordance with instructions in the Trial Supply Manual.

9 STATISTICAL METHODS

9.1 Determination of Sample Size

In a previous trial (000145) comparing individualised dosing of FE 999049 with GONAL-F in a GnRH antagonist protocol, the standard deviation for number of oocytes retrieved in subjects from China receiving a starting dose of 150 IU of GONAL-F was 7.5. Assuming the standard deviation in this trial to be 7.5, and assuming the treatments to be equally effective for the primary endpoint (number of oocytes retrieved), a sample size of 133 subjects per treatment group will give 90% power to demonstrate non-inferiority of FE 999049 vs. GONAL-F. This is based on a non-inferiority margin of 3.00 oocytes, a one-sided 2.5% significance level, and was calculated using the normal approximation. A total of 300 subjects will be randomised in the trial to ensure at least 90% power also for the analysis of the per-protocol analysis set.

9.2 Subject Disposition

All subjects screened should be accounted for with respect to allocation to analysis sets and trial completion.

9.3 Protocol Deviations

Major protocol deviations, such as significant non-compliance or other serious unforeseen deviations deemed to invalidate the data for the primary endpoint, will lead to exclusion of data from the per-protocol (PP) analysis set. Data will not be excluded from the PP analysis set in case of minor protocol deviations or protocol deviations not affecting the primary endpoint. The list of major protocol deviations includes, but is not limited to:

- Unblinding of assessor
- Non-compliance with IMP for two or more days
- The hCG for triggering of final follicular maturation was incorrectly administered, resulting in no oocytes retrieved

The rating of protocol deviations in ‘minor’ and ‘major’ will be decided by the Ferring clinical team on the basis of a blinded review of data before declaration of clean file and lock of database. If the blinded review identifies serious unforeseen deviations deemed to impact the primary endpoint, these will also be rated as major deviations.

The list of major protocol deviations will be detailed and documented in the clean file document prior to database release.

9.4 Analysis Sets

9.4.1 Full Analysis Set

The full analysis set (FAS) comprises all randomised and exposed subjects. Subjects will be analysed according to randomised treatment.

9.4.2 Per Protocol Analysis Set

The per-protocol (PP) analysis set comprises all randomised and exposed subjects except those excluded as a result of major protocol deviations as described in Section 9.3. Subjects will be analysed according to actual treatment received.

9.4.3 Safety Analysis Set

The safety analysis set comprises all treated subjects and is analysed according to the actual treatment received.

9.5 Trial Population

9.5.1 Demographics and other Baseline Characteristics

Demographics and other baseline characteristics will be summarised by treatment group.

9.5.2 Medical History

Medical history will be coded using MedDRA and will be summarised by System Organ Class (SOC) and Preferred Term (PT).

9.5.3 Concomitant Medication

Concomitant medication will be coded using the World Health Organisation Drug Reference List and will be summarised by Anatomical Therapeutic Chemical Classification System (ATC) classification 1st level (alphabetically) and ATC classification 2nd level.

9.5.4 Other Safety Evaluations

Physical and gynaecological examination findings will be summarised by treatment group.

9.6 Statistical Analysis

9.6.1 General Considerations

Non-inferiority comparison for the primary endpoint will be performed for both the FAS and the PP analysis set. Other efficacy analyses will be performed for the FAS only. All descriptions of safety data (including the secondary endpoint on OHSS) will be based on the safety analysis set.

Missing data will, in general, not be imputed. For subjects without oocyte retrieval, the number of oocytes, fertilised oocytes, and embryos will be regarded as zero. For pregnancy endpoints, lack of data will be interpreted as a negative pregnancy, unless a subsequent pregnancy endpoint is confirmed to be positive. Missing endocrine values of stimulation day 1 will, when used as covariate, be imputed by the mean of all non-missing values for this visit.

All statistical analyses will be detailed in a Statistical Analysis Plan which will be issued as a separate document and finalised before FPFV.

9.6.2 Primary Endpoint

The primary endpoint, number of oocytes retrieved, will be compared between FE 999049 and GONAL-F using a negative binomial model with treatment and dose level (10 µg/150 IU or 15 µg/225 IU) as factors. The absolute treatment difference in number of oocytes retrieved and the associated two-sided 95% confidence interval will be derived from the model estimates using the delta method. Non-inferiority will be considered confirmed if the lower limit of the 95% confidence interval for the difference between FE 999049 and GONAL-F is greater or equal than -3.00.

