An essential part of ovarian stimulation involves concomitant treatment with GnRH analogues to prevent premature luteinisation and ovulation,² which can be achieved via two different approaches: pituitary desensitisation with prolonged daily administration of a GnRH agonist or instant blockade of the pituitary luteinising hormone (LH) secretion with a GnRH antagonist.^{3,4,5} Both treatments are effective in preventing premature LH surges^{4,6,7} and comparable in respect of clinical outcomes, such as number of oocytes retrieved and live birth rates.^{5,8} Nonetheless GnRH analogues differ in their safety profile,^{9,10} GnRH agonist treatment being associated with adverse drug reactions related to hypoestrogenism and with higher incidence of OHSS compared with GnRH antagonist treatment, especially in predicted normal to high responders.^{5,8,11}

Differently from the algorithmic dosing of FE 999049, which is based on each subject's serum AMH concentration and body weight, the starting dose in conventional dosing of rFSH is commonly based on age, previous IVF outcomes, and markers of ovarian reserve such as antral follicle counts and circulating AMH, follicle-stimulating hormone (FSH), and estradiol concentrations.^{12,13} A starting dose of 150 or 225 IU rFSH is applied in women with anticipated normal ovarian response, 150 IU being applied in women of younger age and expected to have a robust response, and 225 IU being applied in women of older age or in women expected to have a less robust response.^{14,15} The dose is fixed for the initial days of stimulation, followed by the possibility for subsequent dose adjustments.^{14,16}

Previous trials comparing efficacy and safety of a GnRH antagonist protocol with a long GnRH agonist protocol using rFSH derived from Chinese hamster ovary cell lines in conventional dosing have consistently indicated that the cohort of recruited follicles is slightly smaller with the GnRH antagonist protocol. A difference in oocytes of -1.0 (95% confidence interval [CI]: -1.8; -0.2) was observed in the largest randomised controlled trial⁷ which is in agreement with the difference of -1.1 (95% CI: -1.5; -0.6) in a Cochrane review including data from 27 randomised controlled trials.¹⁷

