be fixed for the first five stimulation days. Based on the subject's ovarian response, the dose may be increased or decreased by 75 IU, with dose adjustments implemented not more frequently than once every 2 days. The minimum GONAL-F dose is 75 IU and the maximum GONAL-F dose is 300 IU. Subjects can be treated with rFSH for a maximum of 20 days, and coasting is not allowed.

During stimulation, subjects will be monitored by transvaginal ultrasound on stimulation days 1 and 6 and thereafter at least every second day. When the leading follicle reaches a diameter of ≥ 15 mm, transvaginal ultrasound will be performed daily. Triggering of final follicular maturation with 250 µg hCG (OVIDREL, Merck Serono) will be done as soon as ≥ 3 follicles with a diameter ≥ 17 mm are observed (i.e. on the day or the day after). Triggering can also be done in case 1 or 2 follicles with a diameter ≥ 17 mm are observed and the investigator judges that ≥ 3 follicles with a diameter ≥ 17 mm cannot be reached, and that triggering is preferred instead of cycle cancellation. If there are < 25 follicles with a diameter of ≥ 12 mm, 250 µg hCG will be administered. If there are ≥ 25 follicles with a diameter of ≥ 12 mm, the cycle is to be cancelled (i.e. hCG will be withheld and the subject will not undergo oocyte retrieval). In case of poor ovarian response, defined as the investigator judging that the triggering criterion cannot be reached by day 20, similarly the cycle is to be cancelled. In case of risk of OHSS or any other safety concern by the investigator, the cycle is to be cancelled.

Oocyte retrieval will take place 36h (± 2 h) after triggering of final follicular maturation. All oocytes from follicles with an estimated diameter ≥ 12 mm must be retrieved. The oocytes can be inseminated by IVF or ICSI. Fertilisation will be assessed on day 1 after oocyte retrieval. The number and quality of embryos will be assessed on day 3 after oocyte retrieval. The embryo quality assessment will consist of the following embryo morphology parameters: number of blastomeres, degree of fragmentation, blastomere uniformity and visual signs of multinucleation. A good-quality embryo is defined as an embryo with ≥ 6 blastomeres and $\leq 20\%$ fragmentation without signs of multinucleation, or with cleavage stage classified as compacting / compacted.

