3.5 Discussion of Overall Trial Design and Choice of Control Groups

3.5.1 Trial Design

The primary objective of the trial is to compare FE 999049 at a starting dose of either 10 µg or 15 µg to GONAL-F at a starting dose of either 150 IU or 225 IU in conventional regimens with respect to ovarian response in women undergoing controlled ovarian stimulation in a long GnRH agonist protocol. In China, approved rFSH preparations such as follitropin alfa (GONAL-F) and follitropin beta (PUREGON/FOLLISTIM) have a conventional dosing approach, i.e. fixed starting dose for initial days of stimulation followed by possibilities for subsequent dose adjustments. In contrast, the dosing regimen proposed in the submitted application for FE 999049 in China is based on each woman's serum AMH concentration and her body weight using a GnRH antagonist protocol. The dose selection is further discussed in Section 3.5.4.

A long GnRH agonist protocol is commonly used in Chinese clinical practice and therefore that downregulation protocol will be applied in the current trial. The majority of clinical trial data with FE 999049 has been generated in a GnRH antagonist protocol. Data from a phase 3b trial conducted in EU (Trial 000304), showed that number of oocytes retrieved after controlled ovarian stimulation using an individualised FE 999049 dosing regimen based on serum AMH concentrations and body weight of women, with serum AMH concentrations of ≤ 35 pmol/L, was higher with the long GnRH agonist protocol compared to the GnRH antagonist protocol, with a difference of 1.31 [95% CI: 0.22; 2.40]. The number of oocytes retrieved was influenced by age and serum AMH concentration, and the difference between the protocols was largest for younger patients and for patients with higher ovarian reserve. No differences in incidence of OHSS or in the overall safety profile were observed between the protocols. After controlled ovarian stimulation using the individualised FE 999049 dosing regimen, live birth rate and neonatal health follow-up data collected up to 4 weeks after birth were similar for the two protocols. For reassurance of neonatal health data after controlled ovarian stimulation using the conventional FE 999049 dosing regimen with the GnRH agonist protocol, neonatal health data will be collected up to 4 weeks after birth as follow-up to the current trial.

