6.2 Screening

Potential subjects will be scheduled to come to the clinic for the screening assessments. Screening must be initiated within 90 days before stimulation day 1 (randomisation).

The following must take place during the screening period:

- Signed and dated written informed consent, obtained prior to any trial-related procedures
- Allocation of a screening number
- Check of inclusion and exclusion criteria (those which are possible to check at screening)
- Demographics (date of birth, ethnicity, race)
- Collection of the following data:
 - Relevant medical history (including any cysts)
 - Infertility history
- Body weight and height [*note*: the results will be used for calculation of BMI]
- Physical examination
- Gynaecological examination
- Urinary pregnancy test – must be negative
- Blood collection for central laboratory analysis of:
 - Endocrine parameters (screening panel: AMH, TSH, and prolactin) [*note*: the results must be available before randomisation]
 - Clinical chemistry and haematology parameters [*note*: the results must be available before randomisation]
- Recording of use of any concomitant medication within the last 3 months prior to signed informed consent for participation
- Recording of adverse events (from the date of signed informed consent for participation in the trial)

Subjects considered eligible for the trial based on the inclusion and exclusion criteria assessed at this time point will be provided a subject participation card and proceed to the next visit scheduled on day 21-24 of their menstrual cycle.

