7.3 Other Assessments

7.3.1 Demographics

Demographic information will be obtained during the screening period, including date of birth and confirmation of the subject's ethnicity and race. Subjects must possess a Chinese identification card and have native Chinese parents.

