9.6.3 Secondary Endpoints

Number of Follicles

Total number of follicles, and number of follicles ≥ 10 mm, ≥ 12 mm, ≥ 15 mm and ≥ 17 mm, on stimulation day 6 and at end-of-stimulation will (in separate analyses) be compared between FE 999049 and GONAL-F using the same negative binomial regression model as used for the primary endpoint.

Serum Concentrations of Estradiol and Progesterone

Serum concentrations of estradiol and progesterone on stimulation day 6 and at end-of-stimulation will (in separate analyses) be compared between FE 999049 and GONAL-F using analysis of covariance (ANCOVA) models with treatment and dose level as factors and with the serum concentration on stimulation day 1 as a covariate. Multiplicative models will be used, i.e. the serum concentrations will be log-transformed before analysis. The results of the analyses will be back-transformed and presented as estimated geometric means and mean treatment ratios. Values below the lower limit of quantification (LLOQ) will be estimated with LLOQ/2. Potential values above the upper limit of quantification (ULOQ) will be included as ULOQ.

Number of Fertilised Oocytes and Fertilisation Rate

Number of Fertilised oocytes will be compared between FE 999049 and GONAL-F using the same negative binomial regression model as used for the primary endpoint. The fertilisation rate (number of fertilised oocytes/number of oocytes) will be described for subjects with at least one oocyte retrieved.

Number of Embryos

Number of embryos and good-quality embryos will be compared between FE 999049 and GONAL-F using the same negative binomial regression model as used for the primary endpoint.

Total Gonadotropin Dose and Number of Stimulation Days

Total gonadotropin dose will be summarized by treatment and dose level. Number of stimulation days will be compared between FE 999049 and GONAL-F using an analysis of variance model with treatment and dose level as factors.

Pregnancy Endpoints (Positive β hCG rate, Clinical Pregnancy Rate, Vital Pregnancy Rate, and Ongoing Pregnancy Rate)

Pregnancy endpoints will be compared between FE 999049 and GONAL-F using a logistic regression model with treatment and dose level as factors. The results in terms of odds for pregnancy will be converted into proportions, difference in proportions, and a 95% confidence interval for difference in proportions using the delta method.

Implantation Rate and Ongoing Implantation Rate

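### The primary model leaves out age and AMH, which the protocol itself reports as influencing oocyte yield; adding them is a nearly free precision gain, probably small

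*Combined protocol and SAP*

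**What the plan says.** Section 9.6.2, repeated in the synopsis, compares the arms "using a negative binomial model with treatment and dose level" as factors. The absolute difference and its two-sided 95% confidence interval come from the model by the delta method, and non-inferiority requires a lower limit of at least -3.00 oocytes. Dose level has two categories and is the investigator's choice of starting dose.

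Elsewhere the protocol says the following about age and AMH:

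- Section 3.5.1, on trial 000304 (individualised dosing of FE 999049): "The number of oocytes retrieved was influenced by age and serum AMH concentration". No effect size is given.
- Section 1.1: "the starting dose in conventional dosing of rFSH is commonly based on age, previous IVF outcomes, and markers of ovarian reserve", and AMH is one of the markers listed.
- Section 6.2 puts AMH in the central-laboratory screening panel, with the result required before randomisation. Section 4.1.1 makes AMH of at most 35 pmol/L an inclusion criterion.
- Section 7.3.1: "Demographic information will be obtained during the screening period, including date of birth".

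Section 9.6.1 sets the scoring rule: "For subjects without oocyte retrieval, the number of oocytes, fertilised oocytes, and embryos will be regarded as zero". It also announces a separate SAP, which was not among the documents reviewed. Nothing in the protocol adjusts the primary endpoint for age or AMH or gives a reason for leaving them out.

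**The concern.** The lower confidence limit decides the trial. A baseline variable that predicts oocyte yield beyond dose level removes residual variance and narrows the interval with no extra subjects and no extra data. Age and AMH are the two variables the protocol names as influential, and AMH should be almost complete because eligibility depends on it. Dose level carries part of the same information, but only as a two-way judgement; differences in age and AMH within a dose level stay in the residual.

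The loss matters little if the true difference is 0 and the SD is 7.5. It matters more if FE 999049 yields somewhat fewer oocytes than GONAL-F, where planned power is clearly lower.

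**Working it through.** **The plan's own figure (Section 9.1).** Inputs: margin 3.00, SD 7.5, one-sided 2.5%, power 90%, true difference 0, 1:1 allocation.

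n per arm = 2 × 7.5² × (1.960 + 1.282)² / 3² = 131.3, so 132. The plan states 133, which agrees once a small-sample correction of about 1 is added. Power is 90.4% at 133 per arm and 93.4% at 150.

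**Effect of adjustment.** Let R² be the share of the variance remaining after dose level that age and AMH explain. The documents do not give it; 2% to 15% is an assumption. With d the true difference:

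- SE = 7.5 × √(1 − R²) × √(2/150)
- Power = Φ((3 + d)/SE − 1.96)
- Half-width = 1.96 × SE

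For R² = 0, SE = 7.5 × 0.1155 = 0.866. At d = 0, power = Φ(3/0.866 − 1.96) = 93.4%. At d = −1, power = Φ(2/0.866 − 1.96) = 63.7%.

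| Assumed R² | SE reduction | Half-width | Power, d = 0 | Power, d = −0.5 | Power, d = −1 |
|---|---|---|---|---|---|
| 0 | 0 | 1.70 | 93.4% | 82.3% | 63.7% |
| 0.02 | 1.0% | 1.68 | 93.8% | 83.0% | 64.5% |
| 0.05 | 2.5% | 1.65 | 94.5% | 84.2% | 65.9% |
| 0.10 | 5.1% | 1.61 | 95.5% | 86.1% | 68.2% |
| 0.15 | 7.8% | 1.56 | 96.4% | 87.9% | 70.7% |

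**Check that adjustment is safe.** Negative binomial data were simulated with mean 10 (the expected GONAL-F mean in Section 3.5.1), SD 7.5 and 150 per arm. The difference was averaged over subjects with a delta-method interval, and no cancellation rule was applied.

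- Power without and with the covariate: 93.7% and 93.8% when it explained nothing; 94.5% and 96.5% at R² = 0.10 (1,500 runs each).
- One-sided error at a true difference of −3: 3.1% without and 3.3% with the covariate at R² = 0.20; 3.2% and 3.0% at R² = 0 (3,000 runs each). Both models sit slightly above 2.5%, and adjustment does not make this materially worse.

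**Effect of scoring cancelled cycles as zero.** Section 3.1.2 cancels cycles with 25 or more follicles of at least 12 mm, and Section 9.6.1 then counts zero oocytes. This breaks the relation between AMH and yield at its upper end. An illustrative simulation used 300 subjects, AMH capped at 35 pmol/L, dose level correlated with age and AMH, and three assumed strengths of effect, with 200 runs per setting. The ratio is the adjusted SE divided by the planned-model SE.

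| Dispersion | Cycles cancelled | Added R² | SE ratio |
|---|---|---|---|
| 0.30 | rule not applied | 0.051 / 0.110 / 0.151 | 0.979 / 0.947 / 0.919 |
| 0.30 | 6.0 / 7.3 / 7.9% | 0.015 / 0.029 / 0.034 | 0.999 / 0.994 / 0.990 |
| 0.15 | rule not applied | 0.078 / 0.164 / 0.218 | 0.961 / 0.912 / 0.880 |
| 0.15 | 1.8 / 2.8 / 3.7% | 0.051 / 0.093 / 0.105 | 0.978 / 0.955 / 0.948 |

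With the zero rule the SE reduction is therefore about 0 to 1% in the first setting and about 2 to 5% in the second. Further simulations with other assumed effects gave SE ratios between 0.96 and 1.00. The simulated SDs in the table settings were 4.5 to 7.4, below the protocol's 7.5, and the documents give no cancellation rate.

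In terms of power, a 1% reduction gives SE = 0.857, with 93.8% at d = 0 and 64.5% at d = −1. A 5% reduction gives SE = 0.823, with 95.4% and 68.1%.

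**The case against.** The case for leaving the model alone is that nothing is broken: the analysis is valid, power at 150 per arm exceeds the 90% target, and dose level already reflects age and ovarian reserve. The only prognostic statement comes from a trial that dosed by AMH and body weight, and it gives no size.

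The zero rule also weakens the gain, and the simple R² formula then overstates it. An added R² of 0.029 implies an SE reduction of 1.5%, but the simulation gave 0.6%. The more favourable simulation is also less like this trial: at a mean of 10, dispersion 0.15 gives an SD of √(10 + 0.15 × 100) = 5.0 before covariate effects, and 0.30 gives 6.3, against the planned 7.5. Finally, Section 9.6.3 reuses the primary model for follicle, fertilised-oocyte and embryo counts, so the change spreads, and the unseen SAP might already contain adjusted analyses.

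Most of this stands as a limit on size. The gain may be close to nil, and the 10% and 15% rows should be read as optimistic upper bounds. It does not show that adjustment does harm: the simulations found no visible cost even when the covariate explained nothing. Carrying the same covariates into the secondary counts is harmless if stated. The SAP does not settle the matter, because Section 9.6.2 already names the model. As for the prognostic evidence, trial 000304 also covered women with AMH of at most 35 pmol/L, and the influence was still reported there.

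**Conclusion.** The concern holds as a recommended improvement, not as a defect. The primary model omits two baseline variables that the protocol itself reports as influential and that will be in hand before randomisation.

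The size is uncertain. Under the trial's zero-scoring rule, an SE reduction of about 0 to 5% is the realistic range. At 150 per arm and SD 7.5 that is at most about 2 percentage points of power at a true difference of 0 (93.4% to 95.4%) and about 4 points at −1 (63.7% to 68.1%). These figures rest on assumed covariate effects, assumed dispersion and simulated cancellation rates, none of which the documents supply.

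**What to change.** In Section 9.6.2, the synopsis and the SAP, before unblinding:

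- Add log(screening AMH) and age as continuous covariates alongside treatment and dose level.
- State a rule for AMH below quantification. Section 9.6.3 already has one for estradiol and progesterone: "Values below the lower limit of quantification (LLOQ) will be estimated with LLOQ/2". State a rule for missing AMH too, for example the mean of non-missing values, as Section 9.6.1 does for day 1 endocrine covariates.
- Define the absolute difference as the average, over all subjects in the analysis set, of the predicted counts under each treatment, with a delta-method interval. Section 9.6.2 does not currently say how the difference is averaged, even over dose level.
- Keep the planned model as a sensitivity analysis.
- Say whether the count endpoints in Section 9.6.3 that refer to the primary model take the same covariates.

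The cost is wording and a little analysis work; no new data are needed. The one drawback is reliance on an assumed covariate form, since scoring excessive responders as zero may bend a log-linear AMH effect. The retained sensitivity analysis shows whether the conclusion depends on it.
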